#### 7. Statistical Analysis.

**Phase 3 Data Analysis**. The objectives of phase 3 are to: 1) maintain data files; 2) evaluate study outcomes; and 3) disseminate study results and project materials.

**Data management** Procedures for data management and monitoring will be initiated during the start-up phase. The project coordinator will coordinate the organization and processing of forms, and schedule and implement checks of data quality and completeness. Data from the ACASI files will be saved in the database. Data will be backed up on a regular basis to prevent loss of data. Data will be transferred electronically from the sites to a secure password protected network drives where it will be checked and downloaded. A data-checking plan based on each questionnaire will be used to look for suspicious entries. Data monitoring will be merged as necessary to answer the research questions. [name] will oversee the final quality assurance/quality control data reviews. She will design and conduct the statistical analyses; assist as needed with designing research forms and data entry; and collaborate with the investigators on analysis and interpretation. We have successfully used these procedures in our research projects.

**Sample size and Power Calculation.** For longitudinal analyses of cognitive functioning and biological measures (Aims 1 and 2), our sample size provides adequate power (80%) to detect effect sizes of 0.37 or larger at alpha=0.05. Our ongoing study (Caregiver Stress study) showed that between-group effect sizes related to exercise vs. AC groups are on the order of 0.5 to 0.8 for physiological, physical and psychological functions.

Statistical Analyses. General Considerations in Statistical Analyses: Our initial data exploration will include: 1) determining the distributions of outcome measures and assessing whether data transformations are needed, 2) insuring that the underlying assumptions of statistical analyses are satisfied, 3) identifying potential co-linearity problems, and 4) identifying potential outliers that require further investigation. For categorical variables, we will check for sparse cells and regroup categories if necessary. In building statistical models, we will check linearity assumptions for continuous predictors and consider higher-order terms if needed. *Missing* Data. We will make every effort to minimize missing data by monitoring the degree of missing data regularly and implementing successful methods for obtaining follow-up data. When data cannot be collected, sensitivity analysis will be performed to evaluate the impact of missing data on results. We also plan to use restricted maximum likelihood (REML) method for estimating the longitudinal statistical models to minimize the impact of missing data. This will make it possible to retain cases with partial data while making less restrictive assumptions about missing data patterns. Controlling for Confounding. Our analyses will account for potential confounding factors such as medications, gender, BMI and other specific confounders for each aim. Adjustment for stratification variables. We plan to adjust for the stratification variable, i.e. study site, in the statistical analysis. This will correct for correlation between the treatment groups due to the balanced randomization within each site and consequently provide better statistical power in detecting differences between treatment groups. Adjustment for Multiple Measures and Comparisons. We will apply adjustments such as Bonferroni correction when appropriate to adjust for multiple comparisons. A combination of statistical software will be used for statistical analysis and data visualization, including SPSS (v.20), SAS (v. 9.3), and R (v. 3.0.1). All statistical tests will be two-sided and intent-to-treat procedures will be employed.

AIM 1. Neurocognitive Improvement: We expect the primary cognitive improvements to be found in executive skill, episodic memory, and processing speed (as measured by CANTAB) since these skills are most susceptible to the effects of exercise. As recommended by Grant and Marcotte, demographically adjusted scores will be used to test for intervention effects between the treatment and attention control conditions over the study time period. To adjust for the effects of practice from repeated testing, we develop z-scores for each of the neuropsychological assessment tests using the regression-based method. Specifically, we first use multiple regression from control participants' test scores to derive the norms for change across visit times. Then we calculate the z-score by adjusting the raw test score with the expected normal follow-up score based on the subject's baseline characteristics using the multiple regression model. This method accounts not only for the effects of practice but also test-retest reliability (e.g., regression to the mean, ceiling and floor effects) and is the method suggested for use with clinical samples. The z-scores will be used as the outcome measures in the following statistical analyses. We will then use the confidence-interval-based method to classify whether a subject has shown improved cognitive functioning when comparing to the norms for change. Specifically, we will define "no change" on each cognitive test using a 90% confidence interval (CI) based on the norms generated from the control subjects' data. Then, participants who score above the upper bound of the 90% CI, i.e. in the top 5% of the normal distribution, will be defined as "improved", while those within the 90% CI defined as "no change" and those below the lower bound of the CI defined as "decliners". Modeling and Hypothesis testing. Repeated measures analysis will be performed to model the z-scores of the NP tests, the classified improvement status and other outcome measures longitudinally to test whether there are differences between the two intervention groups in terms of executive skill, episodic memory and information

processing speed at T1 and T3 assessments. Specifically, multilevel models including linear mixed models Version 02.15.2018 Page 18 of 30 (LMM: for continuous outcomes) and generalized linear mixed models (GLMM: for categorical outcomes) will be implemented using SAS (version 9.3; SAS Institute, Cary, NC) where each subject is treated as an experimental unit in the mixed model. An unstructured variance–covariance form will be assumed in repeated measurements within a subject, which provides the most flexible modeling of the covariance structure. Predictors in the models will include 1) visit time 2) intervention group, 3) interaction term between visit time and intervention group and 4) potential confounding factors such as nadir CD4 count, the CPE score (CNS penetration effectiveness of the antiretroviral regimen), ART adherence, time since diagnosis, estimated premorbid IQ, and HAND diagnosis. The fitted mixed model will provide model-based estimates and tests for the outcome measures for the two intervention groups at each time point of the study. Hypotheses tests based on specific contrasts in the mixed model and the interaction term between visit time and intervention group will be performed to test the hypotheses that subjects in the Let's Move program demonstrated improved cognitive functioning as compared to Let's Flex control group.

**AIM 2.** Repeated measures analysis using multilevel models will be performed to test whether there are differences between the two intervention groups in terms of the inflammatory biomarkers, endothelial vascular function and neuronal growth biomarker at T1 and T3 assessments. Prior to fitting the multilevel models, the distributions of the biomarkers will be checked and appropriate transformations will be performed for skewed biomarkers. Similar strategies as in Aim 1 will be used to construct the multilevel models and to perform model-based tests to evaluate the hypotheses in Aim 2.

**AIM 3.** To assess whether the association between the Let's Move program and cognitive function may be potentially or partially mediated by inflammatory biomarkers, BDNF and endothelial vascular function, we will first apply the standard regression-based approach in which several regression analyses are conducted and significance of the coefficients is examined at each step to evaluate the mediation effects. Furthermore, we plan to apply a cross-lagged panel model (CLPM) for longitudinal data to test the mediation effects of the biomarkers at T1 and T3 assessments. The CLPM is a multivariate model based on structural equation modeling (SEM) for testing mediational processes in longitudinal designs. Compared to cross-sectional mediation methods, the CLPM accounts for lagged effects in testing mediation hypotheses in longitudinal data, supports stronger inference about the direction of causation in comparison to models using cross-sectional data, and can reduce the probable parameter bias that arises when using cross-sectional data.

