### Study Assessments.

Cognitive Outcome Measures will be used to measure the primary outcome variables at BL, T1, T2 and T3 assessments. Cognitive outcome measures will be measured at the second visit for baseline after the study cardiologist has cleared a participant to continue with the exercise study after reviewing their EKG from a treadmill stress test. These outcome measures have been effectively used to examine neurocognitive functioning and treatment effectiveness in numerous clinical trials and in persons with wide-ranging medical conditions, including those who have HIV/AIDS. Table 4 lists the selected measures for the proposed study, domains assessed, a brief description of each, primary variable(s), and administration time. The outcome measures reflect the areas of executive functioning, episodic memory, and processing speed hypothesized to be affected by the exercise intervention based on findings in the research literature. Four parallel forms are available for the memory measures to reduce potential practice effects associated with repeated presentation of the same to-be-learned stimuli. [name], the project neuropsychologist, will provide outcome assessment training and continuous monitoring of data collection and quality. The examiner will code the reliability of each test score, any alteration of standard procedure, and the reason.

Table 4. Cognitive Outcome Measures			
Measures	Description	Time (min.)	
Stroop Color and Word Test	The Stroop Color and Word Test consists of a Word Page with color words printed in black ink, a Color Page with 'Xs' printed in color, and a color-Word Page with words from the first page printed in colors from the second page (the color and the word do not match). The respondent goes down each sheet reading words or naming the ink colors as quickly as possible within a time limit. The test yields three scores based on the number of items completed on each of the three stimulus sheets		
Trail Making Test A & B	The Trail Making Test is a neuropsychological test of visual attention and task switching. It consists of two parts in which the subject is instructed to connect a set of 25 dots as quickly as possible while still maintaining accuracy. The test can provide information about visual search speed, scanning, speed of processing, mental flexibility, as well as executive functioning. It is sensitive to detecting several cognitive impairments such as Alzheimer's disease and dementia		

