NIH Toolbox	Computerized cognitive tests developed and distributed by the NIH. Tests include Pattern Comparison Processing Speed Test, Picture Vocabulary Test, Reading Recognition Test, Dimensional Change Card Sort Test, Flanker Inhibitory Control and Attention Test, Picture Sequence Memory Test, List Sorting Working Memory Test, and Oral Symbol Digit Test	

Blood collection procedures: After overnight fasting, all blood samples will be collected with an intravenous (IV) catheter will be placed into a forearm vein or hand. Blood samples will be collected by a research staff or laboratory assistant trained in blood drawing techniques after 30 minutes of rest between 8-11:30 am (to control for circadian variation) in EDTA or Heparin tubes and immediately placed on ice. Where indicated, blood will be spun at 3,000 rpm for 15 minutes at 4C. Plasma samples will be coded, labeled and will be aliquoted into pre-cooled siliconized polypropylene tubes and stored at -80C until assayed for relevant biomarkers. Processing and analyses of specimens will be performed according to manufacturer ELISA recommendations. Blood collection for the measures in Table 5 will occur at **Baseline, T1, T2 and T3 assessments.** When the study is completed, the blood sample will be destroyed.

Flow mediated Dilation (FMD): A forearm test will be conducted to measure endothelial function at **Baseline, T1, T2, and T3 assessments** after overnight fasting. Participants will have a blood pressure cuff placed around one of their arms. The blood pressure cuff will be inflated and deflated and a trained clinical staff will use an ultrasound device to take measurements of the blood flow in the participants arm.

Table 5. Biological Measures			
Measures	Description		
Inflammatory Biomarke	rs		
Soluble Cluster of Differentiation 14 (sCD14)	Marker of monocyte activation, is associated with neurocognitive impairment and HANDs and higher mortality in PLWH. 		
Interleukin 6 (IL-6)	IL-6 is a well-established pro-inflammatory cytokine known to contribute to the pathogenesis of insulin resistance that contributes to increased risk of CVD and CI through inflammation and promotion of endothelial vascular dysfunction. IL-6 has also been associated with both depression and fatigue in both medically ill and medically healthy individuals. 		

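### Aim 1's analysis names an instrument (CANTAB) that is not in the trial's battery, tests at two of the three hypothesised follow-ups, and does not say which contrast or multiplicity family decides the aim

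*Combined protocol and SAP*

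**What the plan says.** **Instrument.** Section 7, AIM 1, expects the primary improvement in "executive skill, episodic memory, and processing speed (as measured by CANTAB"). Section 5, Study Assessments, says that the cognitive outcome measures "will be used to measure the primary outcome variables at BL, T1, T2 and T3 assessments", and that "Table 4 lists the selected measures for the proposed study, domains assessed, a brief description of each, primary variable(s), and administration time". The rows of Table 4 are Stroop, Trail Making, letter and category fluency, HVLT-R, BVMT-R, Grooved Pegboard, Finger Tapping, Coding, three span tests, IADL and the NIH Toolbox. The Toolbox is the only computerised battery ("Computerized cognitive tests developed and distributed by the NIH"). CANTAB is mentioned nowhere else.

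**Outcome.** For each test, AIM 1 states that "we calculate the z-score by adjusting the raw test score with the expected normal follow-up score" and makes these z-scores the outcome. It then adds an improved / no change / decliner classification and plans to "model the z-scores of the NP tests, the classified improvement status and other outcome measures longitudinally".

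**Visits.** H0 1 and H0 2 (Section 4) cover three post-baseline assessments, and Section 5 collects the same measures at T2 as at T1 and T3. The Aim 1 group comparison is of "processing speed at T1 and T3 assessments". Aim 2 and the Aim 3 cross-lagged model use the same two visits. AIM 1 also says that the mixed model will give "model-based estimates and tests for the outcome measures for the two intervention groups at each time point of the study".

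**Deciding test.** AIM 1 tests its hypotheses through contrasts that it does not identify, together with the visit-by-group interaction. The general considerations in Section 7 promise a Bonferroni-type correction where suitable, two-sided tests, and no defined family.

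**The concern.** These passages govern the primary aim. A reader needs to know which scores represent the three domains, at which visit or visits the groups are compared, and which test decides the aim. On the first two points the plan contradicts itself. On the third it offers tests that can answer different questions.

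The interaction matters most. When the outcome exists only at follow-up, a visit-by-group interaction asks whether the group difference changes from one follow-up to the next. It does not ask whether there is a difference. A programme that helps equally at T1, T2 and T3 would then show no interaction. The plan does not say whether baseline is one of the modelled visits, so it cannot be told whether the interaction tests benefit. Leaving the deciding contrast and family open until data are seen would also weaken any claim of control over false positives.

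**Working it through.** **1. The plan's own figure.** Section 7 gives 80% power for effect sizes of 0.37 or more at alpha 0.05. For a single-visit comparison of two means, the detectable effect is (z[1−α/2] + 0.842) × √(1/n1 + 1/n2), with z = 1.960 at α = 0.05 and 2.394 at α = 0.05/3. The sample sizes come from the Abstract, Section 4 and Section 5. The arm labels are reversed between sections, but the formula is symmetric in n1 and n2.

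| Sample | √(1/n1+1/n2) | α = 0.05 | α = 0.05/3 |
|---|---|---|---|
| 132/68 (200) | 0.1493 | 0.418 | 0.483 |
| 160 left, at 132:68 | 0.1669 | 0.468 | 0.540 |
| 107/53 (160) | 0.1680 | 0.471 | 0.543 |
| 128 left, at 107:53 | 0.1878 | 0.526 | 0.608 |

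None gives 0.37. A one-sided test with all 200 does: (1.645 + 0.842) × 0.1493 = 0.371. But the plan is two-sided. A two-sided average of three follow-ups, with variance factor (1+2ρ)/3, gives 0.37 if ρ is about 0.67 with 200 participants. The plan states no contrast and no correlation, so 0.37 can be neither confirmed nor called wrong.

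**2. What adjustment would change (assumed correlations 0.5 to 0.7, α = 0.05).**
- Baseline adjustment multiplies the detectable effect by √(1−r²). The range becomes 0.418 × 0.714 = 0.30 to 0.526 × 0.866 = 0.46.
- Averaging T1–T3 multiplies it by √((1+2ρ)/3). The range becomes 0.418 × 0.816 = 0.34 to 0.526 × 0.894 = 0.47.

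**3. Contrast choice.** Assume a constant benefit of 0.5 SD (the middle of the plan's 0.4 to 0.6) and follow-up scores only. Let δ be the group difference at a visit.
- The interaction null is δ(T1) = δ(T2) = δ(T3). It is true here, so the test rejects at about alpha.
- A single-visit contrast has power Φ(0.5/√(1/n1+1/n2) − 1.960), which is 0.918, 0.850, 0.845 and 0.759 down the table, before any baseline adjustment.
- A simulation (107/53, visit correlation 0.6, 5,000 runs) gave 4.5% for the interaction and 84% for the T3 contrast.
- If baseline is a modelled visit, δ is about 0 there and 0.5 afterwards. The interaction null is then false, and the test is a conventional one for treatment effect.

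**4. Size of the family (illustration only).** Assume one score per domain, each tested two-sided at 5% without adjustment, with success on any domain. Domain and visit correlations are each 0.5 to 0.7 and are multiplied across the two.

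| Family | Independent | Correlated |
|---|---|---|
| 3 domains, one visit | 1−0.95³ = 14.3% | 11–13% |
| 3 domains, T1 and T3 | 1−0.95⁶ = 26.5% | 18–22% |
| 3 domains, three visits | 1−0.95⁹ = 37.0% | 23–29% |

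If all three domains must succeed, this is the wrong error rate. Testing each at 5% already keeps the chance of a false overall claim at one visit at or below 5%.

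**The case against.** Several points on the other side are sound.

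- **CANTAB looks like leftover wording.** It occurs once, in a sentence about what is expected. The operative text models z-scores of the neuropsychological tests, and Section 5 points to Table 4. A reader might infer that the primary analysis cannot be carried out. It can, from Table 4, so this part is a correction of wording. The test-to-domain map should not be called missing either: Section 5 says Table 4 holds domains and primary variables, and those entries may have been lost when the PDF was read.
- **T2 is not dropped.** The model reports every time point. T1 and T3 recur in Aims 1, 2 and 3, which may reflect a deliberate choice. What stands is that this choice disagrees with H0 1 and H0 2.
- **The outcomes are not wholly unranked.** AIM 1 makes the z-scores the outcome before it brings in the classification, although the modelling sentence then lists both.
- **The interaction may be a valid test.** A reader might infer that two analysts would reach opposite primary results. That follows only if baseline is outside the model, which the plan does not say. The plan also promises contrasts and the interaction together, not one or the other. The rejection rate of about 5% is true by construction under the stated condition.
- **The error rates assume no adjustment.** The plan does promise correction where suitable, and it scores each test, not domain composites. H0 1 joins the domains with a conjunction, which may mean that all must succeed. So 37% is not this trial's false-positive rate.

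None of this says which contrast decides Aim 1, over which family, or what part T2 plays.

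**Conclusion.** The point holds. There are two plain contradictions in the analysis: the instrument in Aim 1, and the visits in Aims 1 and 2, with the same two-visit wording in Aim 3. There is also a real gap, because no confirmatory contrast or family is named while the interaction is offered as a test of benefit. That last matter is serious only if follow-up z-scores alone are modelled. In that case a constant benefit leaves the interaction with a rejection rate of about 5%, where a group-difference contrast at 0.5 SD would have 76–92% power.

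The false-positive figures (11–13%, 18–22% and 23–29%) rest on the assumed correlations, one score per domain, no adjustment and success on any domain. A reader might also infer that 0.37 is an error. The documents do not support that, since an averaged or baseline-adjusted contrast could give it. It cannot be checked until the contrast and the correlation are stated. Because the matter concerns the primary aim and cannot be settled credibly once results are known, it should be fixed beforehand.

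**What to change.** 1. In Section 7, AIM 1, replace the CANTAB parenthesis with the Table 4 tests that form each of the three domains. Use Table 4's own domain and primary-variable entries if they exist, and have the project neuropsychologist confirm the mapping.
2. Reconcile the visits in Aims 1, 2 and 3 with H0 1 and H0 2. Either test T1, T2 and T3, or state that T2 is modelled but not confirmatory and amend the hypotheses.
3. Name one group-difference contrast on the z-scores as confirmatory for Aim 1: the T3 difference if lasting change is the question, or the average over T1–T3 if the overall effect is. Do not use the visit-by-group interaction as the test of benefit unless baseline is in the model, and say how it enters.
4. State whether success needs any or all of the three domains. If any, adjust across the three by Holm or Bonferroni. Make the improvement classification, single tests and other visits secondary.
5. Name the contrast and family for the Aim 2 biomarkers.
6. Restate the detectable effect for the chosen contrast and family, with its assumed baseline or within-subject correlation. Without such adjustment, a single-visit comparison detects 0.42–0.53 SD at alpha 0.05 and 0.48–0.61 SD at 0.05/3. Baseline adjustment or averaging would lower these.

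All of this should be settled before any outcome is examined by arm. The cost is SAP wording and a little scoring code, with no new data. The downside is that single-test results become secondary and the stated power may look less favourable.
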